**The hearing threshold** is defined as the lowest audible level, measured twice out of three presentations for that patient. The thresholds at each frequency for each ear for both air and bone pure tone audiometry will be recorded on the e-CRF at each study visit. The information will be captured in case of no response because of profound hearing loss.

The **hearing loss** will be determined as follows: Difference between the mean hearing threshold at the 3 most affected contiguous test frequencies (air pure tone average) and the corresponding mean hearing threshold of the contralateral ear or values from a pre-existing audiogram (dated less than 2 years) for the same frequencies (mandatory for bilateral acute acoustic trauma).

The Pure tone average frequencies determined at baseline will remain fixed for all evaluations. In case of bilateral acute acoustic trauma leading to sudden sensorineural hearing loss, the most affected ear according to the inclusion criteria will be considered for the analysis. If both ears are equally affected, the right ear will be considered.

In case of one missing frequency in any of the post baseline measurement, the PTA will be determined on the 2 out of the 3 available frequencies. An absolute improvement of 10dB is considered clinically meaningful.

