#### **6.1.1 Intent-To-Treat Analysis Set**

The Intent-to-Treat (ITT) analysis set will comprise all randomized patients according to randomization group. All efficacy analyses will be performed on the ITT analysis set.

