**6.2.9 Inexact Values**

In the case where a variable is recorded as “> x”, “≥ x”, “< x” or “≤ x”, a value of x will be taken for analysis purposes.

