### 6.12.1 Primary Endpoint

The primary endpoint is the change in pure tone audiometry (PTA: average of the hearing threshold of 3 contiguous most affected hearing frequencies in decibels as identified at study entry) on pure tone audiometric air conduction testing in the affected ear from baseline to the end of treatment visit (Visit D28 ± 3).

The 3 most affected contiguous audiometric test frequencies are defined with respect to the unaffected contralateral ear and will be fixed for all further calculations. In case of a pre-existing contralateral hearing loss, the corresponding values of a pre-existing audiogram of the affected ear, if dating back less than 2 years, will be considered as the reference. For all other scenarios (e.g. pre-existing contralateral hearing loss with no audiogram in the past 2 years) the reference frequencies will be set using the ISO 7029;2017 norm values. In case of bilateral acute acoustic trauma leading to sudden sensorineural hearing loss, the most affected ear according to the inclusion criteria will be considered. If both ears are equally affected, the right ear will be considered.

At baseline, if 2 or more sequences of 3 contiguous frequencies are similarly affected, the index sequence with the lower contiguous frequencies will be selected as the reference. Pure tone average frequencies determined at baseline will remain fixed for all evaluations.

If one of the frequencies is missing for post baseline values the PTA will be averaged on 2 out of the 3 identified frequencies. If more than 1 is missing, the PTA will not be calculated.

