### **Analysis details**

Descriptive statistics (n, mean, SD, median, Q1, Q3, min, max) of observed data by visit (Day 7, 14, 28) and treatment group (placebo, SENS401 29 mg, SENS401 43.5 mg) displaying baseline, post-baseline, change will be provided.

Mean changes from baseline of the hearing loss at days 7, 14, and 28 will be analyzed using a restricted maximum likelihood (REML)-based repeated measures approach under the assumption of data missing at random (MAR). Analyses will include the categorical, fixed covariates of site category (non-ancillary, ancillary), duration of disease ( $\geq 24$  hours or  $< 24$  hours), and oral

	Sponsor:	Sensorion
	Protocol Number:	SENS 401-201
STATISTICAL ANALYSIS PLAN. PHASE 2-3-4		

corticosteroids intake at baseline (yes or no) as entered in the IWRS and the fixed, categorical effects of treatment, visit (Day 7, Day 14, Day 28), and treatment-by-visit interaction, as well as the continuous, fixed covariates of baseline score and baseline score-by-visit interaction. An unstructured (UN) covariance structure will be used to model the within-patient errors. If this analysis fails to converge, simpler structures such as first-order ante-dependent ANTE(1), first-order autoregressive AR(1), or compound symmetry (CS) will be tested in a model without treatment effect. The covariance structure converging to the best fit, that is, with the lowest Akaike's information criterion (AIC), will be used in the full model. The Kenward-Roger approximation will be used to estimate denominator degrees of freedom. The estimations and standard errors of the contrasts of interest will be derived from this model. For each timepoint the marginal predicted means (Least Squares Means) and corresponding standard error and confidence interval (consistent with the significance level applied for the study part considered) will be displayed (and also graphically illustrated with mean changes on y-axis and time on the x-axis by treatment groups). The p-value of the visit by treatment interaction will be provided. For each timepoint, one-sided p-values for the comparisons with Placebo and for the comparison of high dose versus low dose will also be displayed with comparisons with Placebo at Day 28 being the comparisons of primary interest while the other comparisons are secondary.

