SAS code to perform the analysis described above for part 1 (i.e. when 3 treatment arms are available) is provided below wherein TRT01PN is the treatment group, AVISITN is the analysis visit (Day 7, 14, and 28) as defined in Section 6.2.15, ANCIL is the site category (non-ancillary, ancillary), DHR is the duration of the hearing loss ( $\geq 24$  hours or  $< 24$  hours) strata, and CORT is the intake of oral corticosteroids at baseline (Yes, No) strata. Note that the ordering of the coefficients for the ESTIMATE statements may need to be updated depending on the entry order in the CLASS statement and will be different for the analysis of part 2 (where only 2 treatment arms will be present). Moreover, 'TYPE=UN' may need to be replaced with 'TYPE=ANTE(1)', 'TYPE = AR(1), or 'TYPE=CS' if the model with 'TYPE=UN' failed to converge.

```
proc mixed data = <dataset>;
  class subjid trt01pn avisitn ANCIL DHR CORT;
  model chg = trt01pn avisitn trt01pn*avisitn base base*avisitn ANCIL DHR
  CORT / ddfm = kr;
  repeated avisitn / type = un subject=subjid(trt01pn);
  lsmeans trt01pn*avisitn / cl e alpha = 0.10;
  estimate 'High vs Placebo, day 28'
    trt01pn -1 0 1
    trt01pn*avisitn 0 0 -1 0 0 0 0 0 1 / alpha = 0.10 cl;
  estimate 'Low vs Placebo, day 28'
```

	Sponsor:	Sensorion
	Protocol Number:	SENS 401-201
STATISTICAL ANALYSIS PLAN. PHASE 2-3-4		

```

trt01pn -1 1 0
trt01pn*avisitn 0 0 -1 0 0 1 0 0 0 / alpha = 0.10 cl;
estimate 'Low vs High, day 28'
trt01pn 0 1 -1
trt01pn*avisitn 0 0 0 0 0 1 0 0 -1 / alpha = 0.10 cl;
run;

```

A similar code (with 2 groups only and alpha = 0.05, two-sided p-value) will be used for the analysis of Part 2.

The number of subjects, the affected ear and the type of reference (unaffected contralateral ear, reference values from a pre-existing audiogram, ISO 2017) will be tabulated by treatment group, stratification groups, and overall.

All PTA data will also be listed.

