More specifically, the imputations will be performed in two steps: “intermittent” missing data (a result is missing but one or more results are available at following visits) will be first imputed by a MCMC method using a non-informative Jeffrey’s prior, thus creating 500 partially imputed “monotone” datasets; then, the remaining missing data will be imputed once in each of these 500 “monotone” imputed datasets using the CR approach leading finally to 500 complete imputed datasets.

The two-step MI procedure will be implemented by the following SAS code:

```
proc mi data=<dataset> nimpute=500 seed=32767 min = . . . . -10 -10 -10
max = . . . . . 120 120 120 minmaxiter = 1000000 out=h2;
  where base ne .;
  mcmc impute = monotone;
  var trt01pn ANCIL DHR CORT base Day07 Day14 Day28;
run;

proc mi data=h2 nimpute=1 seed=32767 min = . . . . . -10 -10 -10 max = . . . .
. . 120 120 120 minmaxiter = 1000000 out=h3;
  by _imputation_;
  class trt01pn ANCIL DHR CORT;
  var ANCIL DHR CORT base Day07 Day14 Day28;
  mmar model (Day07 Day14 Day28 / modelobs=(trt01pn = "1"));*"1" = placebo;
  monotone regression;
run;

data h3;
  set h2;
  chg = Day28 - baseline;
run;
```

An analysis of covariance (ANCOVA) model will then be used to analyze this endpoint on each imputed dataset using the following SAS code for Part 1:

```
proc mixed data=h3;
by _imputation_;
  class trt01pn ANCIL DHR CORT;
  model chg = ANCIL DHR CORT base trt01pn / solution;
  lsmeans trt01pn / diff=control("3") cl;*"1" = placebo;
  ods output lsmeans =lsm diffs=lsmdiffs ;
run;
```

	Sponsor:	Sensorion
	Protocol Number:	SENS 401-201
STATISTICAL ANALYSIS PLAN. PHASE 2-3-4		

Uncertainty in the imputations will be reflected appropriately in the analysis by combining the results on each imputed dataset using Rubin’s methodology (Rubin 1987). The final estimate is the mean of the estimates from the 500 imputed datasets, and the final variance is the sum of the average within-imputation variance and (1 + 1 / 500) times the between-imputation variance. From the final point estimate and variance, the 90% CI will be determined. The results aggregation of the MI procedure after analysis of the 500 imputed datasets will be implemented by the following SAS code:

```
proc mianalyze data=lsmdiffs alpha=0.10;
  by trt01pn;
  modeleffects Estimate;
  stderr StdErr ;
run;

proc mianalyze data=lsmdiffs alpha=0.10;
  modeleffects Estimate;
  stderr StdErr ;
run;
```

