***6.12.4.4 Change in speech discrimination threshold from baseline to Day 28, and 84.***

The Speech recognition threshold is the minimum hearing level at which the patient can correctly recognizes the speech stimuli 50% of the presented speech material. Assessments with missing value with "Reason not performed" = "No response due to hearing loss" will be assigned with the maximum observed value in the database.

	Sponsor:	Sensorion
	Protocol Number:	SENS 401-201
STATISTICAL ANALYSIS PLAN. PHASE 2-3-4		

Mean changes from baseline of the speech recognition threshold at Days 7, 14, 28 and 84 will be analyzed using the same modeling approach as for the primary endpoint for both study parts. A line plot will be produced to show the discrimination threshold by timepoint for each treatment group for all individual subjects.

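### SAP 6.12.1 does not separate a pure-tone no-response due to hearing loss from a truly missing frequency, so an ear that did not recover can be scored as improved

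*SAP*

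**What the plan says.** - **Primary endpoint, SAP 6.12.1.** The PTA (pure-tone average) is taken over the three index frequencies chosen at baseline. For follow-up: "If one of the frequencies is missing for post baseline values the PTA will be averaged on 2 out of the 3 identified frequencies". If two or three are missing there is no PTA. Protocol 13.4 has the same rule. Neither text says whether a no-response counts as missing.
- **No-responses are expected.** Protocol 10.1.1 defines the threshold as the lowest level heard, then adds: "The information will be captured in case of no response because of profound hearing loss". It gives no dB value and refers to a separate audiometry manual for detail.
- **The speech threshold has a rule.** In SAP 6.12.4.4 a speech test with no result, where the recorded reason is no response due to hearing loss, "will be assigned with the maximum observed value in the database".
- **Two nearby rules.** SAP 6.2.9 covers results recorded as an inequality such as > x: "a value of x will be taken for analysis purposes". The imputation code in SAP 6.12.3 limits imputed PTA to 120 dB ("120 120 120 minmaxiter = 1000000 out=h2").
- **Blank PTAs.** The primary repeated-measures model (SAP 6.12.2) treats missing values as missing at random.

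**The concern.** A no-response is a very poor result. A frequency that was not tested carries no information. The SAP draws this distinction for speech but not for the thresholds that make up the primary endpoint.

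The speech rule also shows that this database can hold a no-response as a missing value with a reason. If pure tones are held the same way, the follow-up rules read literally do two things:

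- **One no-response:** the worst frequency is removed and the PTA is averaged over the two better ones. The ear looks better than it is.
- **Two or more:** the PTA is blank and is handled as missing at random, although it is blank because hearing is so poor.

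SAP 6.2.9 helps only if the result was entered as an inequality, which no text says. The 120 dB limit applies to imputed values in one sensitivity analysis and gives no value to an observed no-response.

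**Working it through.** **1. Error in one ear.** Let m be the mean of the two measured frequencies and C the value a no-response would be given. Dropping it gives a PTA of m; scoring it gives (2m + C)/3. The difference is m - (2m + C)/3 = -(C - m)/3, always toward improvement when C exceeds m.

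**2. Worked example (assumed thresholds).** Baseline 80/90/105; follow-up 80/90/no response. The documents give no audiometer limit, so C = 110 and C = 120 are both shown.

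- Baseline PTA: (80 + 90 + 105)/3 = 91.67
- Treated as missing: (80 + 90)/2 - 91.67 = **-6.67 dB**
- Scored at 110: (80 + 90 + 110)/3 - 91.67 = **+1.67 dB**
- Scored at 120: (80 + 90 + 120)/3 - 91.67 = **+5.00 dB**

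The third frequency worsened, yet the ear scores as better. Here C - m is 25 or 35 dB, so the error is 8.3 or 11.7 dB. That is at the large end: under the simulation inputs in step 4 a typical affected ear has an error of about 1 to 4 dB.

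**3. Secondary endpoints, same ear.** SAP 6.12.4.1 and 6.12.4.2 pick the two worst and the single worst of the index frequencies, by loss at baseline. With a flat reference ear these are 105 and 90, and 105.

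- Two frequencies, baseline 97.5: 90 - 97.5 = -7.5 dB if the remaining frequency is used, or blank if not (no rule is given). Scored: (90 + 110)/2 - 97.5 = +2.5, or (90 + 120)/2 - 97.5 = +7.5 dB.
- Single frequency: blank, against 110 - 105 = +5 or 120 - 105 = +15 dB.

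These endpoints are second and third in the testing order of SAP 6.12.6.

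**4. Effect on the treatment contrast.** The plan's baseline-adjusted SD reproduces: 30 x sqrt(1 - 0.45^2) = 26.79 dB. At 37 per arm the standard error is 26.79 x sqrt(2/37) = 6.23 dB.

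The documents give no no-response rate, so every simulation input is assumed: mean baseline threshold 75 or 90 dB, between-ear SD 20, between-frequency SD 10, limit 110 or 120 dB, visit noise SD 5. Full recovery is 30% on placebo and 45% on active; other ears improve by a mean of 10 or 20 dB. Each arm has 200,000 ears. The contrast columns use ears with a complete baseline.

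| Mean / limit (dB) | Placebo Day 28: one / two or more no-responses | Contrast, scored | Contrast, as missing | Difference |
|---|---|---|---|---|
| 75 / 110 | 2.3% / 1.4% | -11.71 | -11.68 | 0.03 |
| 75 / 120 | 1.0% / 0.4% | -11.98 | -11.96 | 0.02 |
| 90 / 110 | 5.6% / 5.4% | -12.86 | -12.81 | 0.05 |
| 90 / 120 | 3.1% / 2.1% | -13.51 | -13.48 | 0.03 |

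The follow-up effect is below 0.1 dB in every row. With no drug effect, the scored and missing contrasts agree within 0.06 dB.

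**The case against.** **Storage is inferred.** That pure-tone no-responses are stored as missing is carried over from the speech field. The audiometry manual may set a value. The documents also mention central review of data before an interim look, and a blinded variance review and a first look have been done, so some convention was already in use. The interim and monitoring-committee analyses have their own SAPs, not available here. All this stands. It means the SAP should state or cite the convention, not that the convention is wrong.

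**The effect is negligible.** For the primary contrast, on the assumed inputs, that is right.

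**A sensitivity analysis already covers it.** Only in part. The Copy Reference imputation in SAP 6.12.3 relaxes missing at random for blank PTAs, but fills them from placebo-group data and not at a ceiling. A PTA averaged over two frequencies counts as observed, so that analysis leaves it untouched.

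**Stronger readings a reader might infer.**

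- *The most severe ears drop out at baseline.* The averaging rule covers follow-up only, the model needs a baseline ("model chg = trt01pn avisitn trt01pn*avisitn base base*avisitn ANCIL DHR"), and the ITT set "will comprise all randomized patients according to randomization group". So loss is possible. It is unlikely, because Protocol 8.1 requires a three-frequency mean for entry and choosing the index frequencies also needs numbers. The documents do not support a drop-out or power figure.
- *It is unclear which baseline is subtracted from a two-frequency follow-up.* It is clear enough. SAP 6.2.15, SAP 6.12.1 and the code use one baseline per patient, over three frequencies.

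**Conclusion.** The gap is real. Neither document gives a pure-tone no-response a value, and the missing-frequency rule, read literally, removes the worst thresholds of ears that did not recover. The consequence depends on storage: it arises if a no-response is held as missing with a reason, and not if it is held as an inequality that SAP 6.2.9 resolves.

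For a single ear the error is typically about 1 to 4 dB, and 8.3 or 11.7 dB in the worked example. For the primary contrast it is below 0.1 dB from follow-up values on the assumed inputs, with no type I error concern. A reader might infer that the primary result is at risk; these figures do not support that. The two-frequency and single-frequency secondary endpoints are the most exposed, because they rest on the frequencies most likely to give no response. This is an inexpensive clarification that should be made, because the scoring of non-recovered ears should not depend on an unstated data-entry convention.

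**What to change.** In SAP 6.12.1, before treatment codes are opened, add: Before the missing-frequency rule is applied, a pure-tone no-response due to hearing loss is scored at the highest level tested at that frequency, at baseline and at every visit, including in the two-frequency and single-frequency endpoints. If that level was not recorded, the maximum observed value at that frequency in the database is used.

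The fallback follows SAP 6.12.4.4. If the audiometry manual already sets a value, cite it instead. Keep the existing rule for frequencies missing for other reasons. Tabulate no-responses and blank PTAs by arm and visit.

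**Cost:** a sentence or two and one table, with no new data if the no-response reason was captured as Protocol 10.1.1 says. The level tested may not have been recorded, in which case only the data-dependent fallback operates. The ceiling is a convention: it can differ between audiometers, understates true loss, and may make results in profound cases look slightly less favourable.

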### 13.4 Handling of missing data:

The primary end-point is the absolute change in PTA (in dB) from baseline to the end of treatment visit (D28) based on the average on the 3 most affected contiguous audiometric test frequencies identified at baseline.

The 3 most affected contiguous audiometric test frequencies are the reference and will remain fixed for all further calculations. They are defined according to the unaffected contralateral ear or values of a pre-existing audiogram dated less than 2 years.

At baseline, if 2 or more sequences of 3 contiguous frequencies are similarly affected, the index sequence with the lower contiguous frequencies will be selected as the reference.

If one of the frequency is missing for post baseline values, the PTA will be determined on 2 out of the 3 identified frequencies. If more than 1 is missing, the PTA will not be calculated.

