### **6.2.2 Baseline**

Baseline for efficacy is defined as the last non-missing value (either scheduled, unscheduled or repeat) up to the randomization day included but before randomization date and time. According to the protocol, no data are expected to be collected between the randomization and the first intake of study drug.

Baseline for safety is defined as the last non-missing value (either scheduled, unscheduled or repeat) up to the date of first dose of study drug.

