### 6.2.15 Change from baseline

Change from baseline in absolute terms is defined as the baseline value subtracted from the postbaseline value.

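### When one index frequency is missing at a visit, the plan as written compares a two-frequency PTA with the three-frequency baseline, so audiogram shape enters the change score

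*SAP*

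**What the plan says.** SAP 6.12.1 defines the PTA as the "average of the hearing threshold of 3 contiguous most affected hearing frequencies in decibels as identified at study entry" and adds that "Pure tone average frequencies determined at baseline will remain fixed for all evaluations". For an incomplete later audiogram it says "If one of the frequencies is missing for post baseline values the PTA will be averaged on 2 out of the 3 identified frequencies"; with more than one frequency missing, no PTA is calculated. Protocol 13.4 has the same rule ("If one of the frequency is missing for post baseline values, the PTA will be determined on 2 out of the 3 identified frequencies"), and Protocol 10.1.1 says that "the PTA will be determined on the 2 out of the 3 available frequencies" will be used.

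On the baseline side, SAP 6.2.2 gives one value per patient: "Baseline for efficacy is defined as the last non-missing value". SAP 6.2.15 states: "Change from baseline in absolute terms is defined as the baseline value subtracted from the postbaseline value". The model code in SAP 6.12.2 uses a single `base` variable, and the multiple-imputation code in SAP 6.12.3 computes `chg = Day28 - baseline`. Neither document recomputes the baseline on the two frequencies that remain at the visit.

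**The concern.** The three index thresholds of an ear need not be equal. If one drops out of the visit mean but stays in the baseline mean, the difference mixes any real change in hearing with the shape of the baseline audiogram. Adjusting for baseline PTA in the model does not remove this, because the error depends on how the three thresholds are spread around their mean, not on the mean itself.

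The affected quantity is the primary change score. The Day 84 change, the 10 dB responder endpoint and the >30 dB improvement endpoint use the same PTA. A 10 dB error equals the improvement that Protocol 10.1.1 calls clinically meaningful and the responder cut-off in SAP 6.12.5.4. The three sensitivity analyses in SAP 6.12.3 (per-protocol, copy-reference, rescue) would not reveal it, because a two-frequency PTA counts as observed. The point concerns a frequency that was not measured; how a no-response is scored is a separate matter.

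**Working it through.** The documents state no figure for this error, so there is none to reproduce.

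**Formula.** Let an unchanged ear have index thresholds a, b, c, with c missing at the visit.

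- Baseline PTA = (a+b+c)/3; visit PTA = (a+b)/2.
- Apparent change = (a+b)/2 - (a+b+c)/3 = (a+b-2c)/6.
- With d = c - (a+b+c)/3 = (2c-a-b)/3, the apparent change is -d/2.
- Equivalently, its size is one third of the gap between c and the mean of a and b.

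**Worked ears.** The thresholds are assumptions, because the documents contain no audiograms. All five meet inclusion criteria 3.1 and 3.2 against an assumed flat 10 dB reference ear.

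| Index thresholds (dB) | Baseline PTA | First missing | Middle missing | Last missing |
|---|---|---|---|---|
| 70/70/70 | 70 | 0 | 0 | 0 |
| 60/65/70 | 65 | +2.5 | 0 | -2.5 |
| 50/60/70 | 60 | +5 | 0 | -5 |
| 50/70/90 | 70 | +10 | 0 | -10 |
| 40/70/40 | 50 | +5 | -10 | +5 |

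For 50/70/90 with the 90 missing: (50+70)/2 - 70 = -10 dB, a false gain. With the 50 missing: (70+90)/2 - 70 = +10 dB, a false loss.

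**What 10 dB requires.** A 30 dB gap between the missing threshold and the mean of the other two (30/3 = 10), or an even slope of 20 dB per step with an end frequency missing (20/2 = 10). An even slope of 5 or 10 dB per step gives 2.5 or 5 dB. The formula has no ceiling: a 45 dB gap would give 15 dB.

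**Effect on an arm mean.** One 10 dB error among the 37 patients of a Part 1 arm shifts the mean by 10/37 = 0.27 dB. For scale, with the 26.79 dB standard deviation in Protocol 13.5.1, the standard error of the difference is 26.79 × √(2/37) = 6.2 dB.

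**Effect as noise.** Assume 5% to 10% of patients carry errors of ±10 dB with mean zero. The variance rises from 26.79² = 717.7 by 5 to 10, so the standard deviation becomes 26.88 to 26.98 dB, an increase of less than 1%.

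**If missingness did differ by arm.** Assume a net excess of 2%, 5%, 10% or 20% of patients in one arm, each with a 10 dB error in the same direction. The treatment difference moves by 0.2, 0.5, 1.0 or 2.0 dB, which is 1.3% to 13.3% of the planned 15 dB. The documents support no particular value in this range.

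**After the fix.** Averaging visit minus baseline over the two frequencies measured at both times gives (a+b)/2 - (a+b)/2 = 0 for every unchanged ear.

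**The case against.** - **No sentence prescribes the mismatch.** It follows from reading SAP 6.12.1 with 6.2.2 and 6.2.15, and the sponsor's programs may already match frequencies. This stands as a caution about what the programs do. It does not rescue the text, because the shortening is confined to post-baseline values and the baseline is a single fixed value.
- **Large errors need unusual ears.** This stands. Gentle slopes give about 2 to 5 dB, flat ears none, and a missing middle frequency on an even slope none.
- **The primary comparison is barely touched.** This stands. Protocol 10.1.1 requires all eight air-conduction frequencies, and the trial is double-blind.
- **The classification endpoints decide nothing.** They are exploratory and descriptive (SAP 6.12.5), and raw PTA data are listed, so affected patients can be found. This limits the consequence but leaves the primary change score wrongly derived for those patients.

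A reader might infer that the error always favours improvement, or the drug. The documents do not support that. Direction depends on which frequency is missing: in a 40/70/70 ear, losing the 40 gives (70+70)/2 - 60 = +10 dB, a false worsening. Nor do they say that no-response frequencies are treated as missing. Protocol 10.1.1 says no-response from profound loss is captured. The SAP gives no scoring rule for it on PTA, but that silence does not show that the worst frequency is dropped.

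**Conclusion.** The point holds as a flaw in the derivation of the primary endpoint. Applied as written, the rule produces a spurious change of -d/2 in an unchanged ear: 0 dB if flat, about 2 to 5 dB on gentle slopes, about 10 dB if steep or notched. The sign is a gain when the highest threshold is missing and a loss when the lowest is.

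Its weight in the trial is modest. With no stated rate of single-frequency missingness and no reason to expect a difference between arms, the main effect is small added noise, plus possible misclassification on the 10 dB responder and >30 dB improvement endpoints. Setting a 10 dB single-patient error against the planned group differences of 15 dB (Part 1) or 10 dB (Part 2) would suggest a bias in the treatment effect that the documents do not show. The sizes rest on assumed audiograms and, for the group-level figures, assumed frequencies of occurrence. The formula itself rests on nothing beyond the plan's definitions.

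**What to change.** In SAP 6.12.1, for the change-based endpoints (primary change, Day 84 change, 10 dB responder, >30 dB improvement), state: when one index frequency is missing at a visit, change is the mean of visit minus baseline over the two index frequencies measured at both times. Keep the three-frequency baseline PTA as the covariate. In the multiple-imputation code, derive change for such visits the same way instead of subtracting the three-frequency baseline. Record this in SAP section 8 as a clarification of Protocol 10.1.1 and 13.4, and check that the separate Data Monitoring Committee SAP, which governs the Part 1 efficacy analysis for the committee, uses the same derivation.

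For the absolute-level endpoints (<20, >35 and >90 dB), keep the mean of the two measured thresholds and flag those patients. Do not substitute baseline plus change. A 40/60/80 ear measured at 10/10/missing has a mean change of (-30-50)/2 = -40 dB, so it would be scored 60 - 40 = 20 dB and fail the <20 dB recovery rule although both measured thresholds are 10 dB.

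The cost is a short text change and a small programming change, with no new data, since thresholds are recorded by frequency at each visit. The downside is that a two-frequency change may differ from the three-frequency change when the ear's shape alters during recovery.
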